At first the whole slide image (WSI) is divided into thousands of tiles. These are examined by a convolutional neural network (CNN) to extract tile level features. We will be using Resnet, a common deep learning model used for computer vision as the CNN. The CNN will be trained with multiple instance learning (MIL) at the tile level and later the predicted scores will be aggregated for the WSI level. The final model will be conducted on the slides, to distinguish between R vs. NR. The classifier will be developed on the training cohort, modified if required following processing of the validation cohort and finally tested for efficacy on the test cohort. Cross-Validations techniques will also be used.

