## 8. Scientific methods and sample size

The statistical method to define a required sample size for an AI-based algorithm development is not clearly defined at this point. Our target sample size ( $n=200$ ) is based on several approaches of calculations. Firstly, based on our experience with similar type of studies. For example, an AI algorithm predicting the response to immunotherapy based on digital pathology was developed based on a set of 76 cases in total. An alternative approach is based on our goal of a classifier with final ROC-AUC value of 0.75 or above with the null hypothesis value to be 0.5. We are aiming for a type 1 error value of 0.05 and for a power of 90%. Approximately 20% of patients are fast progressors (PD within first year of treatment). Total sample size required based on these assumptions is 96 with 16 fast progressors and 80 responders (calculated by MedCalc). Considering our goal to produce a highly robust classifier, and considering the relative lack of

robust manners to calculate sample size, we'll aim for a sample size that is roughly 2-3 times larger than the mentioned numbers, and have set therefore our goal as n=200.

AI-based analysis of images of the training cohort will be conducted using various methods, including machine-learning and deep learning methods. The methods deemed to provide optimal separation between R and NR will be utilized further and validated on the validation cohort and lastly on the test cohort. Training/validation/test sets will be derived from the entire study samples and split about 70:15:15.

Classification of the cases to R and NR in each phase of the study, on each of the three cohorts (training, validation and test) will be examined for dependence on potential confounders by multivariate analysis. Covariates to be considered include: age, sex, BMI, smoking status, time from diagnosis of advanced disease to ALK inhibitor initiation, specific ALK inhibitor used, ALK-fusion of variant 3 or other, co-mutations, histology, method of ALK-fusion analysis, presence of brain metastasis, site of tissue analysis and site of section scanning. Each of these additional clinical/molecular parameters will be utilized if available for more than 70% of the cohort.

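### The confounder check ordered on the training cohort, if run on fitted predictions, says little about whether the classifier depends on confounders

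*Protocol*

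**What the plan says.** Section 8 of the protocol fixes both the object and the place of the check. The object is "Classification of the cases to R and NR in each phase of the study". The place is all three cohorts: the classification "on each of the three cohorts (training, validation and test) will be examined for dependence on potential confounders by multivariate analysis". Thirteen covariates follow, among them the drug used, fusion variant, co-mutations, brain metastasis and the sites of tissue analysis and scanning.

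Section 5 describes the fitting: "The classifier will be developed on the training cohort, modified if required following processing of the validation cohort", with the test cohort last. Section 8 adds a selection step on the training images: "The methods deemed to provide optimal separation between R and NR will be utilized further".

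Cross-validation appears once, in section 5: "Cross-Validations techniques will also be used". It is not tied to the confounder check. The sizes come from section 8: "have set therefore our goal as n=200" and "Training/validation/test sets will be derived from the entire study samples and split about 70:15:15".

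The regression form is not stated. Two forms are possible: the classification as outcome with confounders as predictors (form A), or true R/NR status as outcome with the classifier score and confounders as predictors (form B).

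**The concern.** The check is ordered on cases whose labels were used to fit the model and to choose the method. A deep network trained on about 140 slides can come close to reproducing those labels. Its output on those cases is then largely the label itself, and any analysis of that output is largely an analysis of the label.

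Whether the image adds to known predictors is central to this study. The protocol's background wants the classifier to pick out candidates for more aggressive treatment, and section 5 itself describes variant type and co-mutations as potential confounders. A check that cannot separate a classifier working through those factors from one that does not gives no usable answer. It can mislead in either direction: a false alarm under form A, or false reassurance under form B.

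**Working it through.** The protocol states no figure for this check, so there is none to reproduce.

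**Sizes (section 8 split; NR shares of 32% from section 5 and 20% from section 8).**
- Training: 0.70 × 200 = 140 cases; NR = 0.32 × 140 = 44.8 or 0.20 × 140 = 28.
- Validation and test: 0.15 × 200 = 30 cases each; NR = 0.32 × 30 = 9.6 or 0.20 × 30 = 6.
- NR per listed covariate (13): training 44.8/13 = 3.4 or 28/13 = 2.2; each held-out cohort 9.6/13 = 0.7 or 6/13 = 0.5.

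**Limiting case.** Let Y be the true label, S the classifier output and C a confounder. If the model memorises the training cases, S = Y.
- Form A, S on C, becomes Y on C. It returns the label-confounder association whatever the image contains.
- Form B, Y on S + C, becomes Y on Y + C. S explains everything and nothing is left for C.

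**Simulation 1 (assumed model).** Training n = 140 and 30 held-out cases. One binary confounder at 50% prevalence, with NR rates of 47% vs 17% or 40% vs 24% (both average 32%). Ridge linear score on 1 to 300 features, one carrying the confounder and the rest noise, so there is no independent image signal. Five folds, linear regressions, 300 runs per setting. Share of runs with p < 0.05, over both pairs of NR rates unless stated:

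| Check | 1 feature, fitted | 20–300 features, fitted | 20–300, out-of-fold | 20–300, held-out n = 30 |
|---|---|---|---|---|
| Form B: score significant after adjusting for C | 4–5% | about 100% | 11–19% | 3–7% |
| Form A: score depends on C (47% vs 17%) | 100% | 96–100% | 28–99% | 12–82% |
| Form A: score depends on C (40% vs 24%) | 100% | 59–86% | 12–80% | 6–50% |

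With 20 to 300 features the training AUC was 0.75 to 1.00, while the held-out AUC was 0.50 to 0.59.

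The out-of-fold 11–19% counts both directions. A repeat of this setup with 600 runs gave 8–16% in either direction and 4–10% in the positive direction only. A separate setup (10 to 200 features, logistic likelihood-ratio test, positive direction) gave 82–100% with fitted scores and 3–9% out-of-fold.

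**Simulation 2: does form A's dependence mean anything?** Assumed n = 140, 32% NR, binary confounder with 40% prevalence and log odds ratio 1.2 with the label, ridge score, 400 runs. The image carries no confounder information:

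| Features | Fitted scores flag dependence | Out-of-fold scores flag dependence |
|---|---|---|
| 20 | 20% | 4–7% (range over the three settings) |
| 50 | 47% | |
| 200 | 90% | |

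With 200 features the fitted check flagged 91% of runs when the image did carry the confounder, and 90% when it did not. At that degree of overfitting the check does not discriminate.

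**The case against.** Four points can be made for the plan.

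1. Fitted scoring is inferred from silence. Cross-validation is planned and could supply out-of-fold scores, and such detail is often left to an analysis plan, which is not at hand. This stands in part. But the protocol itself names the training cohort as a place for the check, and "The classifier will be developed on the training cohort". Followed as written, that means fitted predictions.

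2. A reader might infer that the training check will make the classifier look independent of confounders, so that a confounded classifier passes. The documents do not support this. It needs both overfitting and form B, and the natural reading of section 8 is form A. Under form A, an overfitted score still showed dependence in 59% to 100% of runs in simulation 1. Without overfitting, form B gave false independence in only 4% to 5%. What remains is that under form A the flagged dependence comes largely from the labels and need not reflect what the classifier uses.

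3. The same sentence orders the check on validation and test cases, which are not used for fitting. This stands. The test cohort is the clean one, since the classifier may be modified after validation. Both are very small for 13 covariates, so they do not replace a sound check on the development cases.

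4. A reader might also infer that the training result will carry most weight because that cohort is largest. Nothing in the protocol ranks the three checks or sets a pass rule.

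Section 8 also plans shuffling of cases across centers and technical features during learning. That addresses center and technical effects. It does not address drug, variant or brain metastasis, and it does not make fitted predictions honest.

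**Conclusion.** The point holds in a limited form. The protocol places a confounder check on the cases used to fit the classifier and does not ask for out-of-fold predictions. If the network overfits, that check is uninformative about what the classifier uses. Under form A it mainly reproduces the label-confounder association, with false flags in 20% to 90% of runs against 4% to 7% out-of-fold. Under form B it is biased towards apparent independence, at about 100% of runs against about 11% to 19% out-of-fold.

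These rates depend on assumptions outside the protocol: one binary confounder, its prevalence and strength, and a ridge score standing in for the network. The direction follows from the limiting case and does not depend on those choices. The size does, and it shrinks as overfitting shrinks. The documents do not support saying that the training check favors the classifier by construction.

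**What to change.** Add to section 8 that, for the development cases, the confounder check uses out-of-fold predictions, with each case scored by a model not trained on it, taken from the cross-validation planned in section 5. The method selection has to be repeated within the folds, or the scores will still be partly fitted. Add that fitted training predictions will not be used as evidence for or against dependence on confounders. State which regression form is meant.

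The cost is a sentence or two of text and a little more analysis work. The association with outcome will look weaker than on fitted predictions. Out-of-fold scores from a heavily overfitted model will also detect a real dependence less often (12% to 99% of runs in simulation 1 with 20 to 300 features), so a non-significant result should not be read as proof of independence.

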### 4. Origin of the data/biological material

Secondary use and analysis of data.

Potential centers that will participate in the study include any Oncology center that can provide H&E images of diagnostic specimens of ALK+ NSCLC patients with clinical follow up of at least a year. It is expected that each center will be able to contribute 10-20 cases, thus to reach a sample size of 200, about 15 centers are required.

**Ethics:** Each participating center is independent and will receive approval of the local IRB.

**Patient data confidentiality:** No identifying information regarding participating patients will leave each of the centers. Participants will be given a study code, the key connecting the code to the patients' identity will be kept at each participating site secured as per local regulations of each site.

[figure not shown]

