### 5. Study conduct

- 1) Participating centers will secure an ethics and administrative approval for retrospective collection of clinical data, and provision of a single H&E stained FFPE section. ALK positive patients will be identified from the working database of each center, data will be collected locally, deidentified and collected centrally. Data collected will include demographics (age, sex, smoking status, co-morbidities, BMI), tumor characteristics (histology, ALK testing utilized, specific test results, co-mutations if known, ALK fusion partner and variants, brain metastasis) and treatment (ALK inhibitor utilized, date initiated, dose reductions, treatment breaks, date of documented progression, date of death or last follow-up). We will aim to include only or mostly patients with NGS results available, to allow for robust and valid identification of the ALK-fusion, as well as the variant type and co-mutations, all proven potential confounders. Next, the required H&E slides will be stripped from identifying details, coded. The scanning of pathology slides will be performed; alternatively, the option of sending the image files instead of the slides themselves is available.
- 2) Image analysis and AI development will be carried out at the Sheba Medical Center, in-house development. The clinical data will be analyzed, tagging study samples as belonging to a responder (R), vs. a non-responder (NR). For the purpose of this study, a NR will be defined as a patient that has progressed or died on an ALK inhibitor treatment within the first year of treatment. Considering most patients would be on alectinib as first-line ALK inhibitor, we expect about 32% of the samples to belong to the NR group. A 30-

70 to 40-60 split between two classes is a reasonable split for the development of a classifier.

The study cases will be randomly split to three: a training cohort, a validation cohort and a test cohort. The cohorts will be stratified by the response to treatment (i.e. equal proportion of R vs. NR cases in each cohort). Next, scanned images will be processed and analyzed. Slides analysis would be done using python using the pytorch packages. Further statistical analysis will be done with R statistical programming.

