In addition, technical parameters such as precise fixation technique, width of sections, type of scanner and similar factors may have significant influence of the image analysis, and care will be taken not to integrate such factors into the algorithm. The generation of the classification algorithm will include at the learning phase repeated shuffling of the cases from various centers and different technical features, thus preventing biased classifications.

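### Shuffling cases does not prevent centre or scanner bias, and a case-level split leaves the test AUC unable to show it

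*Protocol*

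**What the plan says.** Protocol section 8 names fixation technique, section width and scanner type as possible influences on the image analysis and promises that "care will be taken not to integrate such factors into the algorithm". The one concrete step it gives is, at the learning phase, "repeated shuffling of the cases from various centers and different technical features, thus preventing biased classifications".

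The cohorts are formed as follows:

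- Section 5: "The study cases will be randomly split to three: a training cohort, a validation cohort and a test cohort". Also: "The cohorts will be stratified by the response to treatment". No other stratification factor is named.
- Section 8: "Training/validation/test sets will be derived from the entire study samples and split about 70:15:15".
- Section 4: "It is expected that each center will be able to contribute 10-20 cases", with about 15 centres for 200 cases.

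Two further provisions bear on the point. Section 5 adds that "Cross-Validations techniques will also be used", without detail. Section 8 plans a multivariate check of the R/NR classification in each cohort, and its covariates include "site of tissue analysis and site of section scanning".

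**The concern.** Shuffling changes the order or grouping in which cases are presented. It does not change which centre a slide came from, how that centre's slides look, or how many of its patients progressed within a year. If NR rates differ between centres, a network that picks up the centre's look gains real discrimination in these data that has nothing to do with the tumour.

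A test set would expose this only if its slides came from centres the network had not learned. Here the test set carries the same centre-outcome link as the training set. The reported AUC could then be partly centre recognition, which would not carry over to a new hospital, and the written plan contains no AUC that separates the two. The protocol itself treats this risk as serious and then declares it dealt with.

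**Working it through.** The protocol gives no figure for this claim, so there is none to reproduce.

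**Inputs from the protocol.** N = 200; about 15 centres of 10–20 cases (section 4); split 70:15:15 (section 8); NR rate 32% (section 5) or 20% (section 8); AUC goal 0.75 (sections 2 and 8); one-year event rates of 31.6% on alectinib and 22% on lorlatinib (section 1).

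**Assumed.** The SD of the NR log-odds between centres, ranged over 0, 0.3, 0.5 and 0.75. Around 32%, one SD either side means NR rates of about 26–39% (SD 0.3), 22–44% (0.5) and 18–50% (0.75), from logit⁻¹[ln(0.32/0.68) ± SD].

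**Step 1: are test centres seen in training?** The test cohort has 0.15 × 200 = 30 cases, about 2 per centre. Training has 140, about 9 per centre.

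- For a test slide from a centre of 10 cases, the chance that none of the other 9 is in training is about 0.3⁹ ≈ 0.00002. Practically all test slides come from learned centres.
- A centre of average size (200/15 = 13.3) has no test slide with probability about 0.85^13.3 ≈ 0.115, so about 15 × 0.115 = 1.7 centres are absent from the test cohort. That does not help, because the slides that are present come from known centres.

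**Step 2: what can a score earn that knows only the centre?** The score for a case is its centre's training NR proportion, shrunk to the overall rate m: (NR count + 4m)/(cases + 4). It contains no tumour information. Results from 4,000 simulated studies per setting, with the response-stratified 70:15:15 split:

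| Between-centre SD (assumed) | 0 | 0.3 | 0.5 | 0.75 |
|---|---|---|---|---|
| Mean test AUC, NR 32% | 0.499 | 0.532 | 0.571 | 0.624 |
| Share of test cohorts with AUC ≥ 0.75, NR 32% | 1.5% | 2.9% | 6.7% | 14.8% |
| Mean test AUC, NR 20% | 0.498 | 0.524 | 0.563 | 0.615 |
| Share with AUC ≥ 0.75, NR 20% | 2.8% | 5.0% | 9.2% | 17.7% |
| Mean test AUC, NR 32%, half of centre labels random | – | 0.506 | 0.519 | 0.540 |

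The 1.5% and 2.8% at SD 0 are the chance level for so small a test set. Permuting the training cases left the scores identical, so shuffling has no effect on this score.

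**Step 3: a spread taken from the protocol.** Suppose 8 centres have the alectinib rate and 7 the lorlatinib rate. This is extreme, since section 5 expects mostly alectinib. The simulated mean test AUC is 0.519, and 2.9% of test cohorts reach 0.75. If the network could tell the two groups apart perfectly:

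- share of NR cases in the first group: 8 × 0.316/(8 × 0.316 + 7 × 0.22) = 0.621
- share of R cases in the first group: 8 × 0.684/(8 × 0.684 + 7 × 0.78) = 0.501
- AUC = 0.5 + (0.621 − 0.501)/2 = 0.56

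**Step 4: does grouping by centre remove it?** With five folds of three centres, and no centre in both the learning and the evaluation part, the same score has a mean per-fold AUC of 0.500 at SD 0, 0.5 and 0.75. Scores must not be pooled over folds: pooling gives 0.42, 0.40 and 0.38, because a fold with many NR cases leaves a lower NR rate in the data it is predicted from.

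**Step 5: precision of the alternatives.** Binormal score, true AUC 0.75, independent scores:

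| Estimate | SD, NR 32% | SD, NR 20% |
|---|---|---|
| 30-case test cohort | 0.097 | 0.110 |
| 2–3 held-out centres | 0.101 | 0.120 |
| Fold-averaged AUC, about 170 cases | 0.042 | 0.050 |
| Centre-stratified AUC, about 170 cases (about 403 within-centre pairs at NR 32%) | 0.044 | 0.052 |

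Real cross-validated scores are correlated, so the last two rows will be somewhat less precise in practice.

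**The case against.** **The added gain is small.** The planned classifier reads morphology, so what matters is how much centre knowledge adds to tumour signal. With a tumour score of true AUC 0.70 (an assumption) and the centre's log-odds added to it, mean test AUC for tumour alone against tumour plus centre is 0.698 against 0.667 (SD 0), 0.699 against 0.680 (0.3), 0.702 against 0.697 (0.5) and 0.696 against 0.726 (0.75). With ideal weighting the gain is about 0.002, 0.01 and 0.03 at SD 0.3, 0.5 and 0.75, beside a test-cohort SD of about 0.10. This stands: for a classifier with real signal, material inflation needs a large spread between centres and near-perfect centre recognition. It does not rescue the written claim, and it offers least comfort where tumour signal is weak, which is the case the test set should detect.

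**Site is checked elsewhere.** The multivariate analysis includes site of tissue analysis and site of scanning. That may flag dependence, chiefly in the roughly 140 training cases. In the test cohort it has about 6 (20%) to 10 (32%) NR cases for 13 listed covariates and about 15 centres, and it does not correct the AUC.

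**Cross-validation detail belongs in the SAP.** Agreed, and silence on fold structure is not the fault. The fault lies in what section 8 asserts and in the split that sections 5 and 8 fix.

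**Grouped cross-validation describes refitted models, not the final one, and the test AUC stays as it is.** True. The grouped result therefore belongs beside the test AUC and does not replace it.

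**Conclusion.** The concern holds. The statement that shuffling prevents biased classification is wrong, and with a case-level split stratified only by response the test AUC cannot tell tumour signal from centre signal. Both follow from the text and need no assumption about size.

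Inflation is possible, not certain. It is nil if NR rates are equal across centres. For a score with centre knowledge alone, the mean test AUC is 0.53–0.62 over assumed SDs of 0.3–0.75, with a 3–15% chance of reaching 0.75 against 1.5% by chance (NR 32%). These figures assume error-free centre recognition and are a ceiling in that sense. The protocol's own drug contrast gives 0.52, or 0.56 if the two groups were told apart perfectly. The problem should be fixed before model development begins. It does not invalidate the study.

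**What to change.** 1. **Section 8:** delete the closing clause that says shuffling prevents biased classifications. Shuffling itself can stay.
2. **Section 5:** replace the cross-validation sentence with text such as: *Cross-validation will be grouped by centre over all centres (for example 5 folds of 3 centres) on the training and validation cases. No centre will lie in both the learning and the evaluation folds, tuning included. The AUC will be computed per fold and averaged, not on scores pooled over folds. A centre-stratified AUC of the out-of-fold scores (R–NR pairs within a centre, pooled over all centres) will be given with it.*
3. **Reporting:** give both beside the test-cohort AUC, and rest any claim of freedom from centre or scanner bias on them.

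Keep the 70:15:15 split. A single test set of 2–3 held-out centres is not recommended as the sole main result, since its SD is about 0.10 and it depends on which centres are drawn.

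**Cost.** Text and code only: no new data, and the test cohort stays untouched. The model is refitted per fold and the AUC may come out lower. Folds balance less exactly: with 5 folds of 3 centres at 32% NR, the lowest and highest folds average about 23% and 42% NR by chance alone, and more if centres differ. If centres share a scanner, grouping by centre does not test transfer to a new scanner, and the report should say so.
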